5.4.2 Treatment exposure

Total treatment duration [days]:

Date of last administration of any trial medication – date of first administration of any trial medication + 1.

As the date of first administration corresponds to the first intake of xentuzumab or everolimus or exemestane, total treatment duration includes the run-in period in the phase Ib part. Total treatment duration therefore also includes time when treatment was temporarily discontinued and subsequently reintroduced.

Duration of specific medication exposure [days]:

Date of last administration of specific medication – date of first administration of specific medication + 1.

Duration of specific medication exposure will be calculated separately for xentuzumab, exemestane and everolimus.

Number of courses initiated [N]:

Course initiated means that the patient received at least one administration of trial medication in the initiated course.

Total number of xentuzumab infusions [N]:

Sum of xentuzumab infusions calculated across all courses.

It will be calculated for each patient who received at least one infusion of xentuzumab.

Proprietary confidential information © 2018 Boehringer Ingelheim International GmbH or one or more of its affiliated companies

Number of patients with at least one dose reduction

Number of patients with at least one dose reduction will be counted.

The number of patients with at least one dose reduction will first be calculated for any medication and then separately for each specific medication for which dose reduction is allowed. This means that it will be calculated separately for xentuzumab and everolimus.

Time to first dose reduction of specific medication [days]:

Date of first administration of the first reduced dose of specific medication – date of first administration of specific medication + 1.

Time to first dose reduction will be calculated only for patients who had a dose reduction.

This will also be calculated separately for patients with a dose reduction of xentuzumab or everolimus.

Total dose of specific trial medication [mg]:

Total dose of trial medication will be calculated separately for xentuzumab, exemestane and everolimus.

For xentuzumab, this is the sum of the administered doses calculated across all courses and this takes into account the dose reductions.

For exemestane and everolimus, this is calculated as the total duration of treatment with this medication in days multiplied by the actual dose taken (using the actual dose recorded on the Case Report Form (CRF)) for the days the medication was taken. This takes into account the dose reductions of everolimus.

This calculation is only an approximation of the total dose taken, since the way the data are collected does not allow a more precise calculation.

Dose intensity of specific trial medication during all treatment duration (%):

Dose intensity of trial medication will be calculated separately for xentuzumab, exemestane and everolimus:

$100 * (\text{Total dose of specific trial medication actually received by a patient} / \text{Planned total dose of specific trial medication during the entire duration of treatment})$.

The planned total dose is calculated as the total dose of the medication a patient should have received from the date of first administration of the medication to the date of last administration.

The planned total dose of xentuzumab for each patient is calculated using the following formula: planned dose per infusion (e.g. 1000 mg) multiplied by number of visits with administration of xentuzumab.

For exemestane and everolimus, the planned total dose for each patient is calculated using the following formula: total duration of treatment with this medication in days multiplied by the planned daily dose (e.g. 10 mg, using the dose the patient was assigned (Phase Ib part) or randomised to (Phase II part)).

This is done assuming that the initial dose was taken throughout, and dose reduction as specified in the protocol will not be considered in the calculation. This means that if a patient

[figure not shown]
Proprietary confidential information © 2018 Boehringer Ingelheim International GmbH or one or more of its affiliated companies

[figure not shown]
had protocol-defined dose reduction due to an AE, the reduced dose will not be used in the calculation of the denominator.

For everolimus and exemestane, this calculation is only an approximation of the dose intensity, since the way the data are collected does not allow a more precise calculation.

Proprietary confidential information © 2018 Boehringer Ingelheim International GmbH or one or more of its affiliated companies

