#### 4.1.1 Identity of BI investigational product and comparator products

##### 4.1.1.1 BI 836845 (investigational product)

Substance:	BI 836845 human monoclonal antibody
Pharmaceutical form:	Liquid formulation
Source:	Boehringer Ingelheim Pharma GmbH & Co. KG
Unit strength:	10 mg/ml of BI 836845 supplied in 20 ml vials (200 mg/vial)
Weekly dose	1000 mg, 750 mg (starting dose)
Posology:	Once weekly administrated through one hour intravenous infusion. Infusion duration may be extended to over one hour and up to a maximum of three hours in cases of grade $\geq 2$ infusion reactions
Route of administration:	Intravenous infusion. Appropriate dose of BI 836845 will be diluted in isotonic sodium chloride solution (0.9%)
Duration of use:	Continuous weekly dosing (days 1, 8, 15 and 22 in a 28-day course) in the absence of disease progression, intolerable AEs or other reason necessitating withdrawal

Detailed preparation and handling of BI 836845, including information on infusion equipment and infusion procedure, will be described in ISF.

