##### 4.1.4.1.1 BI 836845

Patients will start treatment with their assigned dose tier (see [Section 4.1.3](#)) or RP2D of BI 836845 from course 1 day 1. BI 836845 will be administered at the investigator site intravenously over one hour with a constant infusion rate on the treatment day as specified in the [Flow Chart](#). If scheduled infusion of BI 836845 is not performed within the time window, this treatment will be skipped and will not be made up. Subsequent visits should follow the original visit date schedule. Mannitol is used in the formulation of BI 836845, so an infusion duration of less than one hour must be avoided. The infusion time may be extended to over one hour and up to a maximum of three hours in cases of CTCAE grade  $\geq 2$  infusion reactions (see [Section 4.4.2](#) for grading and management of infusion reactions). Further information on infusion equipment and procedure is described in the ISF. In case of a delay or an interruption of infusion, the reason and the exact time of deviation must be recorded in the eCRF. The accuracy of this information is crucial for the proper evaluation and appraisal of the pharmacokinetics and other data.

**At days of PK sampling during the Phase I and II part, everolimus and exemestane should be administrated within 5 minutes after start of BI 836845 infusion.**

Detailed information of dispensation, preparation, and handling of BI 836845 will be described in ISF.

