Stomatitis, non-infectious pneumonitis, and metabolic events including hyperglycemia and dyslipidemia are common side-effects of everolimus listed on drug label. Please refer to the current everolimus prescribing information for dose adjustment recommendations (except for the Course 1 of the Phase I part where DLT occurs, in which both drugs need to be interrupted until AE recovery, refer to [section 5.2.6](#)). When these AEs occur and are considered related to study treatment, first dose modification is recommended to be made to everolimus preferentially.

No dose reduction is allowed below 500 mg for BI 836845 or 2.5 mg every other day for everolimus.

Alternative dose modification scheme can only be considered after discussion and agreement between the investigator and the BI clinical monitor.

Management of everolimus related adverse reaction and dose adjustment should be based on the European SPC or current prescribing information for everolimus of respective country or institutional standard, except for the Course 1 of the phase I part, for which, protocol should be followed in case of DLT.

Patients who need to reduce the dose of the same drug for more than two times should be discontinued from that drug treatment. Exception to this in patients who derive obvious clinical benefit according to the investigator's judgement could be considered upon discussion with BI's Clinical Monitor.

During temporary treatment interruption of BI 836845, the scheduled drug infusion will be missed and will not be administered retrospectively.

Proprietary confidential information.

© 2016 Boehringer Ingelheim International GmbH or one or more of its affiliated companies. All rights reserved.

This document may not - in full or in part - be passed on, reproduced, published or otherwise used without prior written permission.

In the event of any unrelated AEs or related non-DLT AEs, the study drug(s) may be interrupted for up to 28 days, but no dose reduction should occur unless indicated in the current drug label/SPC of everolimus or exemestane. Otherwise, the decision to continue with the study treatment will be made by the BI Clinical Monitor in agreement with the investigator.

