#### **4.3.1 BI 836845**

BI 836845 will be administered as a single infusion under supervision of the investigator or dedicated study personnel. In the event that the full dose of BI 836845 is not administered to the patient, it must be documented and explained.

A maximum of three BI 836845 infusions may be skipped for the recovery from AEs. Missing BI 836845 treatment for any other reasons is considered non-compliant.

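### SAP 5.4.2 gives two conflicting denominators for xentuzumab dose intensity; read literally, the formula hides skipped infusions

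*SAP*

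**What the plan says.** SAP 5.4.2 defines dose intensity for each drug as 100 times the total dose received divided by the planned total dose. The general rule for the denominator begins: "The planned total dose is calculated as the total dose of the medication a patient should have received from the date of first administration", and the period runs to the last administration. The section then gives drug-specific formulas.

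- **Xentuzumab denominator:** "planned dose per infusion (e.g. 1000 mg) multiplied by number of visits with administration of xentuzumab".
- **Everolimus and exemestane denominator:** "total duration of treatment with this medication in days multiplied by the planned daily dose". The SAP calls the results for these two drugs approximate.
- **Xentuzumab numerator:** "this is the sum of the administered doses calculated across all courses and this takes into account the dose reductions".

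The denominator is to use the initial dose throughout, so protocol-defined reductions do not lower it. Nothing is said about infusions that were due but not given.

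In the protocol xentuzumab appears as BI 836845. Section 4.1.1.1 sets the schedule: "Continuous weekly dosing (days 1, 8, 15 and 22 in a 28-day course". Missed infusions are expected and are not replaced. For one not given within its window, section 4.1.4.1.1 says that "this treatment will be skipped and will not be made up". During an interruption, section 4.1.4.3 says that "the scheduled drug infusion will be missed and will not be administered retrospectively". Section 4.3.1 adds: "A maximum of three BI 836845 infusions may be skipped for the recovery from AEs".

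**The concern.** The general rule and the xentuzumab formula agree only for a patient who skips nothing between first and last infusion. A due but skipped infusion counts in the denominator under the general rule. Under the formula as worded it does not count, because no administration took place at that visit. Since it adds nothing to the numerator either, it disappears from the ratio.

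This matters because interruption without reduction is an expected pattern. For unrelated events and related non-DLT events, protocol 4.1.4.3 permits interruption for up to 28 days and, apart from what the everolimus or exemestane label indicates, no dose reduction. The literal formula cannot register that pattern.

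The three drugs would also be reported on different bases. Everolimus and exemestane denominators run over calendar days from first to last dose, so days off drug lower their percentages. If all drugs are paused together, xentuzumab could look uninterrupted beside a backbone drug that plainly was interrupted. Two programmers following different sentences of the same section would also obtain different figures.

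**Working it through.** The documents report no dose-intensity figure, so there is nothing to reproduce. The check compares the two denominators on the same dosing histories.

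**Inputs**

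- D = planned dose per infusion; 1000 mg is the SAP's own example.
- N = weekly infusions due from first to last administration (schedule from protocol 4.1.1.1).
- s = infusions skipped in that period and not made up (protocol 4.1.4.1.1 and 4.1.4.3).
- G = sum of doses given (SAP 5.4.2).
- Values of N and s are assumed.

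**Formulas**

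- As written: 100 × G / [D × (N − s)]. This is the mean dose per infusion given, divided by the planned dose.
- By the SAP's definition: 100 × G / (D × N).
- Ratio of the first to the second: N / (N − s).

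If every infusion given is a full dose, G = D × (N − s). The formula as written is then 100% whatever s is, while the definition gives 100 × (N − s) / N.

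**Results (D = 1000 mg)**

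| Assumed history | G (mg) | As written | By definition |
|---|---|---|---|
| 12 due, none skipped, full dose | 12,000 | 100% | 100% |
| 24 due, 1 skipped, full dose | 23,000 | 100% | 23/24 = 95.8% |
| 24 due, 3 skipped, full dose | 21,000 | 100% | 21/24 = 87.5% |
| 12 due, 3 skipped, full dose | 9,000 | 100% | 9/12 = 75.0% |
| 47 due, 3 skipped, full dose | 44,000 | 100% | 44/47 = 93.6% |
| 24 due, 3 skipped, 9 at 1000 mg, 12 at 750 mg | 18,000 | 18,000/21,000 = 85.7% | 18,000/24,000 = 75.0% |
| 12 due, none skipped, 5 at 1000 mg, 7 at 750 mg | 10,250 | 85.4% | 85.4% |
| 12 due, none skipped, one infusion of 500 mg | 11,500 | 95.8% | 95.8% |

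The 47-infusion row corresponds to the planning median PFS of 10.8 months in protocol 7.6: 10.8 × 365.25 / 12 / 7 = 46.96 weeks. Three skips is the number protocol 4.3.1 names for recovery from adverse events.

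The last two rows show that the denominators agree when nothing is skipped, so only skipped infusions separate them.

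**Comparison with everolimus.** Twelve weekly infusions span 11 × 7 + 1 = 78 days. If everolimus is also paused for 21 of those days and otherwise taken in full, its dose intensity is 57/78 = 73.1%. For the same three-week pause, xentuzumab is 100% as written and 75.0% by the definition.

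**The case against.** The best counter-argument is that the xentuzumab formula means visits at which the flow chart schedules an infusion. It is offered as the way to compute a quantity just defined as what was due, and SAP 5.4.2 separately defines the total number of xentuzumab infusions. Had the authors wanted that count in the denominator, the term was available. On this reading the conflict vanishes. The reading is possible, but the text does not state it, and the phrase more naturally describes infusions that took place. Counting attended visits would not repair it either, because protocol 6.2.2 lets visits be skipped during an interruption; only a count based on the schedule matches the definition.

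The SAP also refers to a technical TSAP and table shells that are not public. These may resolve the point, so it is not shown that a reported figure would be wrong. The public SAP should still not carry two rules for one number.

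Finally, the sizes are illustrative. Xentuzumab was stopped on 28 October 2016, so the 47-infusion case may be long for many patients. Protocol 4.3.1 does not say whether its limit of three applies per interruption or in total. Both points stand. They affect how large the discrepancy would be, not how it arises.

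It is also fair that the consequence is small. The infusion count, total dose and exposure duration are defined in the same section, and SAP 7.3 lists missed doses by patient. A careful reader could recover roughly how many infusions were skipped.

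**Conclusion.** The concern holds. As worded, the xentuzumab denominator departs from the definition it is meant to implement and removes skipped infusions from the ratio. The result is overstated by the factor N / (N − s) for any patient who skips infusions and then resumes: 24/21 = 1.14 for 3 skips in 24, and 12/9 = 1.33 for 3 skips in 12. It is unchanged for a patient with no such skips. Skips after the last infusion fall outside the period under either rule.

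This rests on the literal reading and on assumed skip counts. The effect is limited to one percentage, summarised descriptively under SAP 7.7. No efficacy or adverse-event analysis in the SAP uses it. It should be corrected because the clinical trial report is intended to inform later trials of the drug, but it does not bear on the trial's main conclusions.

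**What to change.** Replace the xentuzumab formula in SAP 5.4.2 with: planned dose per infusion × number of scheduled weekly infusion visits (Days 1, 8, 15 and 22 of each 28-day course) from the first to the last xentuzumab administration, whether or not the infusion was given.

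The count is well defined because the protocol calculates all visit dates from Course 1 Visit 1. Infusions not given after the sponsor stopped xentuzumab are not counted, because the period ends at the last administration.

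The cost is one SAP sentence and one derivation, using data already collected. If the formula would otherwise have been programmed literally, reported xentuzumab dose intensity falls wherever patients skipped infusions and resumed.

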5.4.6 Electrocardiogram (ECG) assessments and variables

Please refer to [Section 9.2.1](#) for derivation of ECG variables. The generic term QTc for heart rate corrected QT intervals comprises the fixed corrections QTcF (Fridericia's correction) and QTcB (Bazett's correction) intervals. The term 'on-treatment' refers to all scheduled ECG recordings following the first administration of study medication until end of the residual effect period (see also [Section 6.1](#)).

Continuous endpoints

- Changes in QTcF interval between baseline and on-treatment
- Absolute QTcF intervals at baseline and on-treatment

The above endpoints will also be computed for the variables QTcB, uncorrected QT interval, heart rate, PR interval and QRS complex. Furthermore, the percentage change will be calculated for PR interval and QRS complex.

Categorical endpoints

- QTcF intervals ≤ 450 msec, > 450 to ≤ 480 msec, > 480 to ≤ 500 msec or > 500 msec at baseline and maximum on-treatment value
- QT intervals ≤ 500 msec, > 500 msec at baseline and maximum on-treatment value
- Maximum change from baseline to on-treatment value in QTcF interval ≤ 30 msec, 30 msec $<$ QTcF interval ≤ 60 msec, > 60 msec
- Maximum change from baseline to on-treatment value in QT interval ≤ 60 msec, > 60 msec
- Increase of the PR interval from baseline $\geq 25\%$, when the corresponding PR interval is > 200 msec
- Increase of QRS complex from baseline $\geq 25\%$, when the corresponding QRS complex is > 110 msec

Proprietary confidential information © 2018 Boehringer Ingelheim International GmbH or one or more of its affiliated companies

The categorical endpoints based on the QTcF interval will be derived for the QTcB interval correspondingly.

Notable findings are defined as

- QTcF change from baseline to on-treatment value > 60 msec at any time on-treatment
- new onset of QT/QTcF > 500 msec, where “new onset” denotes the occurrence of a finding on-treatment which was not present at baseline

Morphological (qualitative ECG) assessments will include

- qualitative ECG findings, like new onset of rhythm, conduction, ST segment, T and U wave findings, evidence of myocardial infarction, etc., where “new onset” denotes the occurrence of an on-treatment finding, while at baseline this finding was not observed.

Proprietary confidential information © 2018 Boehringer Ingelheim International GmbH or one or more of its affiliated companies

6 GENERAL ANALYSIS DEFINITIONS

6.1 TREATMENTS

Phase Ib: Patients will be analysed according to the cohort initially assigned. All planned analysis will be presented by this cohort, unless specified otherwise. Handling of patients where cohort assignment has not been followed will be handled on a case-by-case basis, to be agreed at report planning meetings or Database Lock (DBL) meeting (but prior to DBL).

Phase II: For safety analyses, treated patients will be analysed according to the treatment they actually received. For efficacy analyses, the Intent-To-Treat (ITT) approach will be used, i.e. patients will be analysed according to the treatment group they were randomised to.

For safety summaries, data recorded during the Residual Effect Period (REP) will be considered as on-treatment. For this trial, the length of the REP is 42 days.

The actual study periods and treatment codes are defined in a document entitled “8-07-other-sdtm-trial-arms-trial-elements”, which can be found in Data Management and Statistics (DMS) folder, Section 8, within Boehringer Ingelheim Regulatory Documents for Submission (BIRDS).

6.2 IMPORTANT PROTOCOL VIOLATIONS

No per protocol set (PPS) analysis will be performed for this study, hence, no patient will be excluded from the analyses (except those with missing informed consent or not adhering to age limit). However patients with potentially important protocol violations (IPVs) will be documented. The following list of potentially IPVs in Table 6.2: 1 will be used; note that this is a working list and may not be finalised until the final Blinded Report Planning Meeting (BRPM) or DBL meeting (but prior to DBL for the primary analysis). Potentially IPVs will be handled according to BI standards [\(6\)](#).

During the study conduct, protocol deviation should be monitored and guidance for improving / teaching the respective sites should be discussed during the study Medical Quality Review Meetings (MQRMs).

Table 6.2: 1 Important protocol violations

Category/ Code		Description	Requirements	Excluded from
A [1]		Entrance criteria not met		
	A1	Diagnosis of trial disease questionable	Inclusion criteria* IN 1 or IN 2 not met.	None

Proprietary confidential information © 2018 Boehringer Ingelheim International GmbH or one or more of its affiliated companies

Table 6.2 : 1 Important protocol violations (cont.)

Category/ Code	Description	Requirements	Excluded from
	A2	Prohibited baseline condition, diagnosis or treatment At least one of inclusion criteria* IN 4- 9 or IN 12 is not met or At least one of exclusion criteria* is met.	None
	A3	Laboratory result indicating inadequate organ function at screening	Inclusion criteria* IN 10 or IN 11 not met
	A4	Adequate archival tumour tissue not available	Inclusion criterion* IN 3 not met.
B [1]		Legal Criteria	
	B1	Informed consent not available / not done	Informed consent date missing or inclusion criterion* IN 13 not met
	B2	Informed consent too late	Informed consent date was after Screening Visit date
	B3	Age limit for patient inclusion not adhered to	Calculate age given the date of birth and date of informed consent. Patients must be ≥ 18 years old.
C		Trial medication and randomisation	
	C1 [2]	Time window violation for procedures performed at screening	Screening imaging earlier than 28 days to first drug intake; Safety labs, ECG performed earlier than 28 days to, or later than first drug intake; Timeframe > 4 days between randomisation and first drug intake

Proprietary confidential information © 2018 Boehringer Ingelheim International GmbH or one or more of its affiliated companies

Table 6.2 : 1 Important protocol violations (cont.)

Category/ Code	Description	Requirements	Excluded from
C2 [2]	Trial medication not given according to protocol	
Dose reduction scheme not followed (see CTP section 4.1.4.3);
 
Administration of trial medication(s) not compliant.
 
Indicated by medical review (i.e. where Administration of xentuzumab according to the protocol = 'No' and associated comments, or compliance data from Exemestane/Everolimus with associated comments)
 
Please note: This excludes the investigational treatment given outside the boundaries specified in the CTP (covered in Category C3)
	None
C3 [1]	Infusion time for the investigational treatment outside of CTP specific boundaries	
Infusion duration of xentuzumab given <50 minutes or >200 minutes (Infusion time should be from 60 to 180 minutes, but the thresholds above are accepted).
 
The exact duration of the infusion should be calculated taking interruptions into account.
 
In case of missing administration times, the violation will not be considered important if administration according to protocol = 'Yes'
	None
C4 [2]	Patient assignment not followed	Patients do not receive the initial treatment they were randomised / allocated to	None
C4.1	Randomisation not followed	This applies only for phase II part of the trial	None

Proprietary confidential information © 2018 Boehringer Ingelheim International GmbH or one or more of its affiliated companies

Table 6.2 : 1 Important protocol violations (cont.)

Category/ Code	Description	Requirements	Excluded from
	C4.2	Treatment allocation not followed Treatment taken at C1V1 is not the treatment assigned at screening.	None
D [2]	Concomitant medication		
	D1	Prohibited treatment during trial conduct phase Treatment taken during the treatment period as described in Section 4.2.2.1 of the CTP. For phase Ib part only, during run-in and course 1: CYP3A4 strong inhibitors, CYP3A4 moderate inhibitors, CYP3A4 strong inducers, CYP3A4 moderate inducers, inhibitors of P-glycoprotein	None
E [2]	Missing Data		
	E1	Imaging assessments not done according to CTP instructions Imaging assessment should be performed at Screening and several time points thereafter (see TSAP Section 6.7.2).	None
F [2]	Trial Specific protocol violations		
	F1	Other protocol violations affecting patient rights or safety Manual Protocol Violations (PVs) will be collectively captured.	None

[1] IPV will be derived automatically

[2] IPV will be identified via individual review at MQRM/Report Planning Meeting (RPM)/DBL.

* During the amendments of CTP the inclusion and exclusion criteria were adapted. Therefore, the inclusion/exclusion criteria valid at subject's enrolment have to be considered.

